Study 046, an international Phase 3 study, was designed to compare ixabepilone plus capecitabine with capecitabine alone in anthracycline-pretreated or resistant and taxane-resistant locally advanced MBC. Participants were required to have measurable disease with tumors that progressed rapidly in the adjuvant or metastatic setting after receiving both anthracyclines and taxanes. Eight percent of patients were receiving first-line treatment, having relapsed within one year of prior anthracycline/taxane therapy in the adjuvant setting; treatment for the remaining 92% of patients was as either second- or third-line therapy. Of the 85% of patients with progression in the metastatic setting following prior taxane, 42% progressed on taxane therapy. A total of 737 patients received ixabepilone (40 mg/m² as a 3-hour intravenous (IV) infusion on Day 1 of a 21-day cycle) plus capecitabine (2000 mg/m² orally administered in two divided doses each on Days 1 through 14 of a 21-day cycle) (n=369) or capecitabine alone (2500 mg/m² on the same schedule as the same schedule) (n=368). The primary endpoint was progression free survival (PFS) evaluated by blinded Independent Radiology Review Committee (IRRC). The addition of ixabepilone to capecitabine resulted in a clinically meaningful and statistically robust improvement in PFS in patients with MBC resistant to anthracyclines and taxanes. The improvement in PFS by the addition of ixabepilone to capecitabine was consistent across subpopulations, including patients with visceral metastases, >2 sites of metastatic disease, \geq 65 years of age, or with HER2+ breast cancer. ¹⁴

CA163048 compared ixabepilone in combination with capecitabine to capecitabine alone in patients with metastatic or locally advanced breast cancer previously treated with anthracyclines and taxanes. A total of 1198 patients were treated: 595 patients received ixabepilone (40 mg/m² as a 3-hour intravenous (IV) infusion on Day 1 of a 21-day cycle) plus capecitabine (2000 mg/m² orally administered in two divided doses each on Days 1 through 14 of a 21-day cycle) and 603 patients received capecitabine alone (2500 mg/m² on the same schedule). In this study overall survival (OS) was the primary endpoint. Results demonstrated statistically significant and clinically meaningful superiority in PFS and improved RR over capecitabine alone that translated into a modest
improvement in OS favoring the combination which did not meet statistical significance.¹⁵

Both Phase 3 studies showed a statistically significant and clinically meaningful improvement in PFS in favor of the combination of ixabepilone and capecitabine over capecitabine alone. Results of these studies showed an improvement in median PFS of 1.6 to 1.8 months and a 21 to 25% reduction in the risk of progression. The benefit in PFS was supported by significant improvements in objective response rate (ORR) in favor of the combination, including a more than doubling of the ORR in CA163046 (35% vs 14%) as assessed by the IRRC. The analysis of OS in both studies showed a 0.9 hazard ratio (HR) favoring the combination that did not reach statistical significance but was consistent with the absence of a detrimental effect. No other Phase 3 studies conducted in patients with breast cancer previously treated with anthracyclines and a taxane have demonstrated a survival benefit.¹⁴

Peripheral Neuropathy

Some subjects in these studies have experienced ixabepilone-related sensory neuropathy that is most often cumulative and reversible. Less frequently, severe motor neuropathy, usually presenting with lower extremity weakness, has been observed. In addition, there have been rare reports of autonomic neuropathy. Neuropathy may be dose- and time dependent. In the event of severe peripheral neuropathy, ixabepilone treatment was to be discontinued and not resumed until the neuropathy returned to baseline or to \leq Grade 1, as defined by the National Cancer Institute (NCI) Common Terminology Criteria for Adverse Events (CTCAE). If the neuropathy was greater than Grade 1, dose reductions were warranted, provided the subject qualified for additional treatment. Peripheral neuropathy was a dose-limiting toxicity in Phase 1 monotherapy studies of ixabepilone at doses above 50 mg/m²every 3 weeks, and cumulative neuropathy has commonly been reported in the Phase 2 studies. The neuropathy is dose dependent and may also be schedule related. The neuropathy is cumulative in nature and gradually lessens following the discontinuation of therapy. Subjects are typically described as presenting with sensory manifestations (dysesthesias

and paresthesias, involving hands and feet). Neuropathic pain has also been reported, although less frequently

(Grade 3/4-related in 3% of 439 subjects treated across all BMS Phase 2 studies). Motor neuropathy has been reported only as a related Grade 3/4 adverse event in 1% of all Phase 2 subjects, and it has only rarely been described in the absence of sensory or painful neuropathy. To date, autonomic neuropathy has been reported in only two subjects, both enrolled in Phase 2 breast cancer studies. One subject developed orthostatic hypotension and gastroparesis after 5 cycles of therapy and the other developed gastroparesis after 14 cycles of therapy. When ixabepilone dose reductions were necessary due to toxicity, the first reduction was to be to a dose of 32 mg/m². The use of the 32 mg/m² dose has been established in at least two other ixabepilone studies: the CA163-011 study of subjects with non-small cell lung cancer and the CA163-116 study of subjects with metastatic pancreatic cancer. A total dose per cycle of 30 mg/m² has also been administered in subjects with breast cancer (6 mg/m2 daily times 5 every 3 weeks) in studies led by the National Cancer Institute.

Hypersensitivity Reactions

The diluent used with ixabepilone is a BMS-purified polyoxyethylated castor oil (Cremophor®EL) and has the potential for inducing a hypersensitivity reaction. In clinical studies of ixabepilone, anaphylaxis and severe hypersensitivity reactions (dyspnea requiring bronchodilators, hypotension requiring treatment, syncope, bradycardia) that were reported as serious adverse events have occurred in less than 1% of subjects. Routine premedication, including H1 and H2 antihistamines (not corticosteroids) was instituted after 2 subjects developed severe hypersensitivity adverse events (dyspnea and bronchospasm) in the weekly Phase 1 monotherapy study. Since premedication was instituted, the incidence of the NCI CTCAE term "hypersensitivity" of any grade is < 1% in 439 subjects treated in all BMS-sponsored Phase 2 studies. In addition, 17% of subjects had a CTCAE term of "allergy/immunology, other" (of any grade) reported; the majority of incidents consisted of skin rash.

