	The study population will include subjects ≥ 18 years of age diagnosed				
	with invasive ductal carcinoma (IDC). Randomization will be stratified by				
disease stage (T1N1-3M0 or T2-4 N0-3M0).					
	Prior to randomization, all patients will have a physical assessment,				
	imaging, a blood draw, and a diagnostic biopsy prior to the start of				
	treatment.				
	The study doctor will determine if the subject qualified to be enrolled in this				
	study. If subjects are enrolled, the duration of their participation is				
	expected to be approximately 6 months				
	Treatment Arm 1				
	Patients will receive Ixabepilone 40mg/m ² given over approximately				
	3-hours on day 1.				
	Patients will receive a total of four cycles of this drug with each cycle				
	given 21 (+/- 3) days.				
	Subjects will be premedicated approximately 1 hour before the ixabepilone				
	infusion with 1) both an oral H1 blocker (diphenhydramine 50 mg or				
	equivalent) and an oral H2 blocker (e.g., ranitidine 150 300 mg or				
	cimetidine 300–800 mg or nizatidine 150-300 mg or famotidine 20–40 mg);				

	or 2) with premedication per institutional standards.			
	Premedication with steroids is indicated in subjects who developed a			
	hypersensitivity reaction to ixabepilone in previous cycles. Patients with			
	severe reaction (see dose modification chart below)should not be			
	retreated.			
	Treatment Arm 2			
	Patients will receive Ixabepilone 40mg/m ² given over approximately			
	3-hours on day 1followed by cetuximab given on day 1 at 400 mg/m ² as			
	an initial loading dose (first infusion) administered as approximately a			
	120-minute IV			
	infusion (maximum infusion rate 5 mL/min) followed by 250 mg/m ²			
	infused over approximately 60 minutes (maximum infusion rate 5 mL/min) as			
	subsequent weekly dose.			
	Patients will receive a total of 4 cycles of this combination with each			
	cycle being 21 (+/-2) days.			
	Subjects will be premedicated approximately 1 hour before the ixabepilone			
	infusion with either 1) both an oral H1 blocker (diphenhydramine 50 mg or			
	equivalent) and an oral H2 blocker (e.g., ranitidine 150-300 mg or			
	cimetidine 300–800 mg or nizatidine 150 - 300 mg or famotidine			
	20–40 mg); or 2) with premedication per institutional standards.			
	Premedication with steroids is indicated in subjects who			
	developed a hypersensitivity reaction to ixabepilone in previous cycles.			

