given in a dose of 40 mg/m² as a 3-hour IV infusion every 3 weeks. A total of 161 subjects were treated. Median age was 55 years. Results in evaluable subjects were Primary Best Overall Response Rate (Complete Response [CR] or Partial Response [PR]): 98/161 (61%); Pathologic Complete Response in Breast [pCR_B]: 29/161 (18%); and Pathologic Complete Response in Breast and Lymph Nodes [pCR_{BL}]: 17/161 (11%). Independent assessment of subject responses yielded pCR_B and pCR_{BL} rates of 14% and 9%, respectively. In subjects with ER-negative, ER-/PR-negative, and triple-negative tumors, as assessed by locally read immunohistochemistry (IHC) and fluorescence in situ hybridization (FISH), investigator-assessed pCR_B rates were 29%, 33%, and 26%, respectively. The pCR_{BL} rates were 19%, 23%, and 19%, respectively.

No deaths were reported. Twelve (8%) subjects reported SAEs. Among these subjects, 10 (6%) reported at least 1 SAE assessed as possibly, probably, or certainly related to ixabepilone therapy. These SAEs included peripheral or sensory neuropathy, febrile neutropenia, neutropenia, vomiting, and hypersensitivity, each reported in 2 subjects; and mucositis, constipation, diarrhea, stomatitis, lymphopenia, leukopenia, thrombocytopenia, increased ALT, and increased AST, each reported in 1 subject.

Treatment-related adverse events were reported in 97% of subjects. The most common (\geq 15% of subjects) were alopecia (86%), myalgia (50%), arthralgia (30%), asthenia (27%), neutropenia (21%), peripheral sensory neuropathy (20%), nausea (19%), fatigue (19%), and diarrhea (15%). Most were Grade 1 to 2. Grade 3/4 treatment-related adverse events were reported in 25% of subjects. The most common Grade 3/4 event was neutropenia (14%).¹²

CA163-081: Phase 2 Study in Refractory MBC

CA163-081 was a single-arm, open-label, multicenter, multinational, two-stage design study of ixabepilone in MBC that was resistant to an anthracycline, a taxane, and capecitabine. A total of 126 subjects were treated. Data from this study have been published. Of the 126 treated subjects, 113 were evaluable for response. Subjects were heavily pretreated: 88% had received \geq 2 lines of prior chemotherapy in the metastatic setting. Independent Radiology Facility (IRF)-

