- Uncontrolled chronic viral infections or patients requiring parenteral antibiotics will be excluded. Patients taking highly active anti-viral therapies and with controlled disease will be allowed to participate.

-Patients with an active, bleeding diathesis or on oral anti-vitamin K medication (except low dose coumadin defined as 1 mg a day)

-Other concurrent and/or uncontrolled medical disease which could compromise participation in the study (i.e., uncontrolled diabetes, uncontrolled hypertension, severe infection, severe malnutrition, unstable angina, or congestive heart failure

- New York Heart Association Class III or IV, ventricular arrhythmias, active ischemic heart disease, myocardial infarction within six months, chronic liver or renal disease, active upper GI tract ulceration).

-Patients with a pre-existing peripheral neuropathy > grade 1.

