7.0 Treatment Plan/Methods

This is a randomized open-label phase II trial; 116 triple negative breast cancer patients will be randomized equally between 1) Ixabepilone or 2) Ixabepilone plus Cetuximab. The study population will include patients≥ 18 years of age diagnosed with invasive mammary carcinoma. Patients will be assigned to treatment arms using a stratified blocked randomization, with strata based on disease stage (T1N1-3M0 or T2-4 N0-3M0). All patients will receive a physical assessment, imaging, a blood draw, and a core needle biopsy (CNB) a biopsy prior to the start of treatment.

7.1 Treatment Arm 1

Patients will receive Ixabepilone 40mg/m² given over approximately 3-hours on day 1 Patients will receive a total of four cycles of this combination with each cycle given 21(+/- 3) days.

Subjects will be premedicated approximately 1 hour before the ixabepilone infusion with either 1) both an oral H1 blocker (diphenhydramine 50 mg or equivalent) and an oral H2 blocker (e.g., ranitidine 150 300 mg or cimetidine 300–800 mg or nizatidine 150-300 mg or famotidine 20–40 mg); or 2) with premedication per institutional standards. Premedication with steroids is indicated in subjects who developed a hypersensitivity reaction to ixabepilone in previous cycles. Patients with severe reaction should not be retreated (see dose modification chart below).

7.2 Treatment Arm 2

Patients will receive Ixabepilone 40mg/m^2 given over approximately 3-hours on day 1 followed by Cetuximab given on day 1 at 400 mg/m² as an initial loading dose (first infusion) administered as a 120-minute IV infusion (maximum infusion rate 5 mL/min) followed by 250 mg/m² infused over 60 minutes (maximum infusion rate 5 mL/min) as a subsequent weekly dose. Patients will receive a total of 4 cycles of this combination with each cycle being 21 (+/-3) days.

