Vehicle for Constitution of Ixabepilone for Injection is supplied with the drug product for use in constitution of the lyophile. Vehicle for Constitution is provided in vials containing 8.0 mL/via (15mg) and 23.5mL (45mg) the vehicle is a mixture of dehydrated alcohol and cleaned Cremophor (polyoxyethylated castor oil). One vial of the 8.0 mL/vial vehicle product is provided whenever a 15 mg/vial of Ixabepilone for Injection is supplied.

Packaging

Ixabepilone for Injection and the Vehicle for Constitution are packaged in Type I glass vials, stoppered with butyl rubber closures and sealed with aluminum seals. A sufficient excess of drug and vehicle is provided in the respective vials to allow for withdrawal losses.

Handling and Dispensing of Investigational Product

The investigational product should be stored in a secure area according to local regulations. It is the responsibility of the investigator to ensure that the investigational product is dispensed only to study patients. The investigational product must be dispensed only from official study sites by authorized personnel, according to local regulations.

Storage Requirements/Stability

Ixabepilone for Injection should be stored refrigerated at 2°C to 8°C (36°F to 46°F) and protected from light. Vehicle for Constitution should be stored at 2°C to 25°C (36°F to 77°F). If the vehicle is refrigerated, it must be allowed to warm to room temperature before constitution of the lyophile. After initial constitution with the accompanying vehicle, the solution may be stored in the vial for a maximum of 1 hour at room temperature and room light. The constituted solution should not be stored in the syringe. After final dilution with Lactated Ringer's Injection, USP (LRI) to ixabepilone concentrations between 0.2 and 0.6 mg/mL, the solution is stable when stored at room temperature and room light for a maximum of 6 hours. Administration of the entire infusion volume must be completed within the 6-hour time period as noted above.

Lactated Ringer's Injection, USP is specified because it has a pH range of 6 to 7.5, which is required to maintain ixabepilone stability. Other diluents should not be used with ixabepilone.

Preparation and Administration

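### Neither exclusion list bars a patient with a known prior severe reaction to a Cremophor product, although both arms receive that vehicle (minor, patient safety only)

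*Combined protocol and SAP*

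**What the plan says.** Section 4.0.2 (Hypersensitivity Reactions) identifies the hazard: "The diluent used with ixabepilone is a BMS-purified polyoxyethylated castor oil (Cremophor®EL) and has the potential for inducing a hypersensitivity reaction". It adds that anaphylaxis and severe reactions reported as serious adverse events occurred in under 1% of subjects in ixabepilone studies. Section 9.0 (Vehicle for Constitution) confirms that this trial's supply uses the same material: "the vehicle is a mixture of dehydrated alcohol and cleaned Cremophor (polyoxyethylated castor oil". Under Sections 7.1 and 7.2 both arms receive ixabepilone 40 mg/m² over about 3 hours.

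On study, Section 7.1 states: "Patients with severe reaction should not be retreated (see dose modification chart below". Section 7.2 repeats the instruction for the combination arm. Premedication in both arms is an oral H1 plus an oral H2 blocker, "or 2) with premedication per institutional standards". Steroids are specifically called for only after a reaction to ixabepilone in an earlier cycle. Footnote o to the schedule in Section 2.0 requires monitoring for hypersensitivity during and after every infusion.

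At entry, the exclusion list appears twice, in the Study Summary and in Section 6.2. Neither version has an item on allergy or hypersensitivity. The nearest is the general exclusion, "Other concurrent and/or uncontrolled medical disease which could compromise participation in the study". The Study Summary leaves the final decision to the investigator: "The study doctor will determine if the subject qualified to be enrolled in this" study. Section 2.2 asks for a medical history and mentions underlying conditions and concomitant medications.

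**The concern.** The protocol treats a severe reaction to ixabepilone as a reason to withhold the next dose. It does not apply that principle at the door. A patient who reports, before enrolment, a severe reaction to a product with the same vehicle meets no written bar to her first study dose. Randomization cannot steer her away from the hazard, because both arms contain the vehicle.

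Only patient safety is at stake. The reactions listed in Section 4.0.2 include anaphylaxis and hypotension requiring treatment, so one avoidable case would matter even if such patients are rare.

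**Working it through.** This is mainly a check of text against text.

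1. **Does every patient get the vehicle?** Yes. Ixabepilone is in both arms (Sections 7.1, 7.2), and its vehicle contains Cremophor (Sections 4.0.2, 9.0).

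2. **Is a prior severe reaction excluded anywhere?** No. Both exclusion lists end with pre-existing neuropathy and contain no item on Cremophor, castor oil, ixabepilone or drug allergy. No inclusion criterion covers it. Parts of the Summary table are broken in the text, but Section 6.2 reads as complete.

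3. **Does the general exclusion catch it?** Not on its wording. It concerns concurrent or uncontrolled disease, and its examples (diabetes, hypertension, infection, cardiac disease and so on) include no allergy. A past drug reaction is not naturally a concurrent disease.

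4. **What protects her at cycle 1?**
   - Investigator judgement (Study Summary): real, but it depends on learning of the reaction, and Section 2.2 does not name prior drug reactions.
   - Premedication: a written rule. The institutional option may include steroids. The specific steroid instruction cannot apply at cycle 1, since it needs a reaction in an earlier cycle.
   - Monitoring (Section 2.0, footnote o): a written rule that covers cycle 1. It detects and limits a reaction but does not prevent exposure.
   - The no-retreatment rule: acts only after a severe reaction on study.

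5. **Could a candidate have been exposed before?** Possibly. No criterion bars prior chemotherapy, and the Summary inclusion list admits second primary breast cancers. The documents name no other Cremophor-containing drug and give no frequency of prior reactions, so no count can be derived.

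6. **Background rates, in patients not selected for a prior reaction.**
   - Serious anaphylaxis or severe hypersensitivity: less than 1% (Section 4.0.2; no denominator given).
   - With premedication, the coded term hypersensitivity "of any grade is < 1% in 439 subjects treated in all BMS-sponsored Phase 2 studies". Since 0.01 × 439 = 4.39, that is at most 4 subjects (4/439 = 0.91%; 5/439 = 1.14%). A further 17% had a separate allergy term, mostly skin rash.
   - In the earlier neoadjuvant ixabepilone study (CA163-080), at the same dose and infusion time: "These SAEs included peripheral or sensory neuropathy, febrile neutropenia, neutropenia, vomiting, and hypersensitivity, each reported in 2 subjects". That is 2/161 = 1.2%, counting serious events judged at least possibly related. The text does not say whether drug or vehicle was responsible.

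7. **Effect on the design.** None. The proposed exclusion changes no sample-size input: 54 per arm, 18% versus 43%, two-sided 0.05.

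**The case against.** The strongest reply is that the affected patient is hypothetical. The documents report no such case, name no other product with this vehicle, and do not say that a reaction to another Cremophor product predicts one to ixabepilone. Prior exposure to ixabepilone itself should be rare among patients with an intact primary tumor who are candidates for preoperative treatment. The history text in Section 2.2 is not exhaustive, and a known severe drug allergy could reasonably count as a relevant underlying condition. A competent investigator would probably ask, and would probably decline to enroll her.

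Much of this stands. It limits the size of the point and makes the added risk to a prior reactor an inference. It does not supply the missing rule: a patient with this history remains eligible as written, on a hazard that the protocol itself identifies and acts on after enrolment.

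A reader might also infer that nothing beyond judgement and premedication protects her. The documents do not support that, because monitoring during and after all infusions is required and premedication is itself a written rule. What is absent is an eligibility rule. Nor should 2/161, whose exact 95% interval runs from 0.2% to 4.4%, be read as the risk to a prior reactor. It comes from one study of unselected patients, and the broader figure in Section 4.0.2 is below 1%.

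**Conclusion.** The point holds as a minor gap in patient protection. A known prior severe reactor to the vehicle is eligible as written, while the protocol advises against any further dose after a severe reaction on study. Three written or delegated safeguards apply at her first dose, but none of them is an eligibility criterion that prevents exposure.

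The number of such patients cannot be estimated and is probably very small. The background rates show that the hazard exists; they do not size this group or its risk. That prior reactors face more than the background risk rests on extending the no-retreatment rule to reactions that occurred before the study, including reactions to other products with the vehicle. This is a plausible clinical inference, but the documents do not state it. Nothing here bears on power, the intention-to-treat analysis or the interpretation of pCR.

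**What to change.** Add to Section 6.2 and to the Study Summary list an exclusion for a known prior severe hypersensitivity reaction to ixabepilone or to another product containing Cremophor/polyoxyethylated castor oil. Define severe by the CTC v3.0 grading already in use (Sections 2.6 and 2.7.1), for example Grade 3-4. A definition is needed because Section 7.1 refers to a dose modification chart for severe reactions, but the ixabepilone tables in Section 7.3.1 have no hypersensitivity row. Limiting the exclusion to severe reactions matches the on-study rules, which foresee continued treatment with steroid premedication after other reactions.

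Add prior drug hypersensitivity to the screening history in Section 2.2, so that the criterion can be applied. The final clinical wording is for the sponsor's clinicians.

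The cost is one line in each of two lists and one history question. The downside is that very few patients are excluded; the sample size and analysis stay as they are.
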